9.8. Data Analysis

The following general approach will be used:

for qualitative data - absolute and relative frequencies will be used. Percentages will be based on the total number of subjects with non-missing values unless specified otherwise. Counts for missing values will be also tabulated but missing values will not be considered in the percentages;

for quantitative data - mean, standard deviation, median, 25th and 75th percentiles, minimum and maximum, and number of non-missing cases (95% confidence intervals for parameters of interest) will be used.

Missing data will not be imputed.

In case of parametric procedures the underlying assumptions will be checked. In case of severe violations of assumptions, nonparametric methods will be used instead.

Exploratory post-hoc subgroup analyses may be performed if appropriate.

All statistical tests will be two-tailed considering a significance level of 5%.

The statistical analysis will account for the panel structure of the data.

Adherence study

Appropriate methods to deal with paired samples will be used. Suitable methods are Generalized Linear Mixed Models (GLMM), such as the Linear Mixed Model (for continuous outcomes, such as ART plus hospitalization costs), Poisson Mixed Model (for count outcomes, such as the number of days covered by treatment) or Logistic Mixed Model (for binary outcomes, such as the proportion of subjects with > 90% adherence). These models might be used as well when analyzing panel data. Other options might be to use Marginal Models (MM) which rely on Generalized Estimation Equations (GEE) for parameter estimation {27761} {27762}.

In order to reduce bias in treatment effect estimation, a propensity score will be obtained and covariate adjustment using the propensity score will be performed. In other words, the propensity score as well as the variable denoting the ART class will be entered in the appropriate regression model (for instance, binary logistic regression).

Prescription errors sub-study

The number of errors will be modeled with Generalized Linear Models (GLM). If significant correlation between hospitalizations from the same subject/hospital is found, then appropriate methods to address such data structure will be used. Suitable methods are GLMM and MM.

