9.1. Study Design

This is a retrospective non-interventional study that has two outcomes: adherence (the primary focus) and prescription errors (sub-study). While all centers will participate in the Adherence study, only centers where prescription data is available will be included in the Prescription errors sub-study. In order to do so, several research hypotheses were formulated:

that SA accounts for a non-negligible portion of OIA and that both SA and NA are clinically and economically relevant

that STRs, as SA-free regimens, will improve adherence, and generate clinical and economic benefits

that STRs are, by nature, of value in avoiding prescription errors.

According to these research hypotheses, study endpoints were established.

Primary endpoint:

Odds of attaining > 90% adherence in the STR cohort versus non-STR cohort, after adjusting for baseline variables and other confounders, with adherence measured by medication possession ratio based on pharmacy refills.

Secondary endpoints:

Adherence

Average OIA and NA levels, in the STR cohort versus non-STR cohort, after adjusting for baseline variables and other confounders, with adherence measured by medication possession ratio based on pharmacy refills.

Average OIA level, according to the number of pills in the regimen (1, 2-3, 4+), after adjusting for baseline variables and other confounders, with adherence measured by medication possession ratio based on pharmacy refills.

Clinical impact

Odds of becoming unsuppressed (HIV RNA >50 copies /mL in two consecutive measures within regimen duration occurring within the observation period) among subjects who had HIV RNA \leq 50 copies/mL between 1st January 2009 and the start of the regimen (whichever is latest); in STR versus non-STR groups, after adjusting for baseline characteristics and other confounders, using laboratory/monitoring data;

Odds of becoming unsuppressed (defined as above) according to subject adherence level (NA and OIA), after adjusting for baseline characteristics and other confounders, using laboratory/monitoring data;

Odds of becoming unsuppressed (defined as above) with resistance development according to subject adherence (NA and OIA), after adjusting for baseline characteristics and other confounders, using laboratory/monitoring data (n.b. may not be feasible).

Hospitalization

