The subjects to be selected are the first ones from each sorted list of the random numbers. For example, if 80 subjects are to be selected in the STR cohort, the top 80 in the list are to be included.

For the selected subjects, check Inclusion and Exclusion criteria. If one subject does not meet the criteria, replace that subject with the next on the list (subject 81 in the example above). Repeat as necessary replacing each subject which does not meet the criteria by the next in the list. The same procedure should be followed if a subject meets the criteria but does not sign the informed consent.

Note that subjects are being selected instead of patient-regimens, so it is not obvious how many patient-regimens will be included. Nonetheless, considering that an average of 1.5 regimens in a 5 year period is likely to occur, then the 700 STR subjects and the 805 non-STR subjects will yield more than enough patient-regimens to reach the required patient-regimen sample size.

A Propensity Score Matching (PSM) approach will be applied subsequently on the merged dataset from all sites in order to maximize homogeneity between cohorts and reduce the impact of treatment-selection bias. A variable ratio between cohorts will be considered, so that 700 STR subjects are selected as cases and 805 non-STR as controls. The propensity score is defined as a subject's probability of receiving a specific treatment (STR) conditional on the observed covariates {27771}. When propensity scores are used in matching, treatment effects are unbiased when treatment assignment is strongly ignorable {27756}. On the other hand, treatment assignment is strongly ignorable if treatment cohorts and the outcome variable are conditionally independent given the covariates. This independence assumption will not hold in situations where there are variables not included as propensity score covariates that are correlated with outcome events and time dependent treatment selection {27757}.

The PSM procedure will include 4 steps:

- 1. Model choice: The propensity score will be computed using binary regression with a logit or a probit link function, depending on model fitting statistics. Statistical based criteria will be used to specify the covariates, such as the degree of association with STR odds.

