9.6. Study Size

Adherence study

The sample size needed to achieve a power of 80% for detecting a difference of 0.02 in the proportion of patients with adherence > 90% (adherent patients) between the two cohorts, with a two sided test with a significance level of 0.05, was determined using the methodology proposed by Sahai and Khurshid {27760}. The number of discordant pairs (the ones with more than 90% adherence in only one of the 2 cohorts) was estimated using data reported in Airoldi et al.{16102}. In this study patients in a non-STR regimen had an average adherence rate of 97% and after changing to an STR regimen a rate of 98%. Assuming the reported standard deviation of 11%, a 0.74 and 0.77 proportion of adherent patients was estimated for non-STR and STR regimens, respectively, which represent the marginal probabilities of adherence. Therefore, if one assumes that patients who adhere to non-STR also adhere to the STR regimen, the probability of adherence to STR conditional to non-adherence to non-STR and non-adherent to STR.

Since a multivariate analysis will be performed, the suggestion by Katz {27773} of adding 10 observations per covariate included in the logistic regression was considered. A potential 20% loss of patient-regimens due to missing values on covariates was considered, as well as an inclusion of 10 covariates in the logistic regression model. In addition a 15% oversampling on the non-STR cohort was considered to enable a final sample size, post PSM, of 1030 pairs of patient-regimens. Hence 700 subjects will need to be included in the STR cohort and 805 subjects will need to be included in the non-STR cohort.

A preliminary evaluation of the availability of the centers to collect data was performed. Taking into account this information, an average of 80 subjects in the STR cohort and 90 subjects in the non-STR cohort, will be needed per center to achieve the power considered in the sample size determination presented above. It is possible that some centers will have less than 80 subjects to include in the STR cohort. In those cases, data from all these subjects should be collected and

other centers may include more than 80 subjects to ensure the overall 2060 patient-regimens sample size is reached.

Prescription errors sub-study

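### The Poisson mixed model named for days covered understates the standard error at the protocol's own adherence SD, unless it carries a patient-regimen-level effect or robust variance

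*Protocol*

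**What the plan says.** Section 9.8 (Data Analysis, Adherence study) introduces generalized linear mixed models as suitable for paired samples and adds that they might also serve for panel data. It gives three examples: a linear mixed model for continuous outcomes such as costs, a logistic mixed model for binary outcomes, and a "Poisson Mixed Model (for count outcomes, such as the number of days covered by treatment"). Marginal models fitted by GEE follow as another option. The section fixes no random-effect level, offset or dispersion term. It says that parametric assumptions will be checked, with nonparametric methods used after severe violations. On error rates it states: "All statistical tests will be two-tailed considering a significance level of 5"%.

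Days covered is not itself a listed endpoint. Section 9.1 lists as secondary "Average OIA and NA levels, in the STR cohort versus non-STR cohort", and section 7.2 defines NA and OIA as proportions of days out of the regimen duration. OIA is therefore one minus the share of days on which all components were held. Section 8.1 also names NA and OIA in the primary objective, but the primary endpoint in section 9.1 is binary (adherence above 90%).

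The only adherence distribution in the document is in section 9.6: "patients in a non-STR regimen had an average adherence rate of 97"%, with 98% after the change to STR, and "Assuming the reported standard deviation of 11%, a 0.74 and 0.77 proportion of adherent patients was estimated".

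**The concern.** A Poisson model allows each patient-regimen's covered days to vary around its conditional mean only with variance equal to that mean. Refill-based coverage does not behave that way. Regimens differ persistently in adherence, so the spread of covered days between regimens grows in proportion to duration, while the Poisson SD grows only with its square root.

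A random intercept protects the cohort comparison only if it sits at the level where the spread arises. The text speaks of paired samples and panel data, which points to intercepts for the matched pair or the subject. Members of a propensity-matched pair are different patient-regimens, usually from different people, so a pair intercept absorbs little. A subject intercept does not absorb differences between regimens of the same subject, and section 9.3 expects some subjects to contribute regimens to both cohorts.

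At stake is the STR versus non-STR comparison of average adherence. If the standard error is too small by a factor of two or more, differences of a fraction of a percentage point would be reported as significant when there is no true effect.

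**Working it through.** **Inputs from the protocol.** Mean 0.97 and SD 0.11 (section 9.6); two-sided 5% (9.8); "final sample size, post PSM, of 1030 pairs of patient-regimens" (9.6); "an average of 1.5 regimens in a 5 year period is likely to occur" (9.3); regimen durations from 90 days to the five-year observation period, about 1826 days (9.3).

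**Assumptions, not in the protocol.** The distribution of durations within that range, within-subject and within-pair correlation, the share of subjects with regimens in both cohorts, and the level of the random intercept.

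**Step 1: reproduce the plan's figures.** Under a normal distribution, P(adherence > 90%) = Φ((97 − 90)/11) = Φ(0.636) = 0.738 and Φ((98 − 90)/11) = Φ(0.727) = 0.766. These agree with the stated 0.74 and 0.77, so 97% and 11% are the protocol's working moments.

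**Step 2: variance ratio.** For duration T, covered days have variance (0.11·T)² and mean 0.97·T. The ratio to the Poisson variance is φ = 0.0121·T/0.97. At 900 days, for example, the SD is 0.11 × 900 = 99 days against √(0.97 × 900) = 29.5 days under Poisson.

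**Step 3: closed-form size.** If the model's variance is too small by φ, the actual two-sided size is 2·(1 − Φ(1.96/√φ)).

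| T (days) | φ, SD 0.11 | size | φ, SD 0.05 | size |
|---|---|---|---|---|
| 90 | 1.12 | 6.4% | 0.23 | about 0 |
| 180 | 2.25 | 19.1% | 0.46 | 0.4% |
| 365 | 4.55 | 35.8% | 0.94 | 4.3% |
| 913 | 11.4 | 56.1% | 2.35 | 20.1% |
| 1826 | 22.8 | 68.1% | 4.71 | 36.6% |

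This uses only the mean and SD, and assumes that the random effect absorbs none of the spread.

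**Step 4: what that means in percentage points.** With 1030 regimens per cohort, 900 days each and no correlation, the smallest difference declared significant is 1.96 × (29.5/900) × √(2/1030) = 0.28 points under Poisson. With the actual SD it is 1.96 × 0.11 × √(2/1030) = 0.95 points.

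**Step 5: simulation with no cohort effect.** Adherence was drawn from a one-inflated beta distribution (mean 0.97, SD 0.11) and days were rounded. The model had a log-duration offset and a Poisson mixed likelihood by Laplace approximation. The pair-intercept fit gave 5.0% on truly Poisson data.

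- Pair intercept (1030 pairs, 300 runs per scenario): 5-7% at 90 days, 18-22% at 180, 34-39% at 365, 50-52% at 912, 63-65% at 1826, and 52-57% with durations uniform on 90-1826 days.
- Subject intercept (about 1.5 regimens per subject, 200 runs; correlation from 0.8 down to 0): 3-16% at 180 days, 9-34% at 365, 31-56% at 912, and 35-67% with mixed durations. In a separate beta simulation the size fell to 6% when no subject had regimens in both cohorts.
- Patient-regimen intercept: 1.5-8% over all SD 0.11 scenarios, with Monte Carlo error of about ±3 points, centred near 4-5%.
- Poisson marginal model with subject-clustered robust standard errors: 3-7.5% at SD 0.11.
- SD 0.05, subject intercept, correlation 0.5: 0.5% at 180 days, 1.5% at 365 and 5% at 912.

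**The case against.** The strongest reply is that the protocol never commits to this test. The Poisson model is one illustration among suitable methods, days covered is not a listed endpoint, GEE is offered in the same paragraph, and the synopsis names only conditional logistic regression, mixed models and marginal models with Gaussian or logistic links. The random-effect level, offset and dispersion are details that usually go in a statistical analysis plan. The unit of analysis is the patient-regimen, and an intercept at that level brings the size back to about 5%. Much of this stands. It limits the point to a named method that is safe only with conditions the text does not state. It does not clear that method, because the stated purpose (paired samples, panel data) suggests the two levels that fail.

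The assumption check would probably expose a variance ratio of 5 to 20. But it leads only to nonparametric methods, or in the synopsis also to transformations. A paired test on the matched sample would keep the adjustment achieved by matching, but not the further covariate and propensity-score adjustment that section 9.8 intends.

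The simulated distribution shares only the mean and SD with the protocol. A plain beta with those moments puts about 92% of regimens above 90% adherence, against 74% in section 9.6. The closed form does not depend on shape and points the same way.

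A reader might infer three stronger claims, and none is supported:

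- **That any Poisson mixed model here has a fixed, large error rate.** It depends on the SD, the durations and the intercept level.
- **That the upper bound on covered days causes the inflation.** A bound alone makes counts under-dispersed and the test conservative: independent days would give φ = 1 − 0.97 = 0.03. The cause is spread between regimens.
- **That the primary result is compromised.** The primary endpoint is binary and is not analysed by this model.

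**Conclusion.** The point holds in a limited form. Section 9.8 names as suitable a model whose variance assumption conflicts with the SD in section 9.6 for all but the shortest regimens. Under mean 97% and SD 11%, and with no patient-regimen effect, dispersion term or robust variance, the two-sided size runs from about 6% at 90 days through 36% at 365 days to 68% at 1826 days by closed form. Simulation gives 52-57% for a pair intercept with durations over the whole range.

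These figures rest on assumed durations and correlations. For a subject intercept they also rest on subjects having regimens in both cohorts. If the true SD were nearer 5% and regimens short, the test would be conservative instead. The consequence is confined to the secondary comparisons of average adherence, so this should be corrected but does not threaten the primary analysis.

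**What to change.** In section 9.8, remove days covered as the example for a Poisson mixed model. State that average OIA and NA will be analysed as proportions of regimen days with the marginal (GEE) model already listed there, using a Gaussian/identity or logistic link as in the synopsis, robust variance clustered by subject, and the same covariates and propensity score.

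If a Poisson model is kept, require a log-duration offset together with either a patient-regimen-level random effect or robust variance.

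The cost is one sentence in the protocol. No new data and no change in sample size are needed. Confidence intervals for the OIA and NA comparisons will be wider than under the plain Poisson model: at 900 days and SD 11% by a factor of about √11.2 = 3.4, and at 365 days by about √4.55 = 2.1.

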9.9. Quality Control

Prior to study start, investigators are required to sign a protocol signature page confirming his/her agreement to conduct this study in accordance with its requirements, and also to give access to all relevant data and records to Gilead (or designee) monitors, auditors, Gilead Clinical Quality Assurance representatives, Ethics Committee and regulatory authorities, if required.

The study site may be subject to review by the Ethics Committee, and/or to quality assurance audits performed by the Sponsor or its designated representative, and/or to inspection by appropriate regulatory authorities. If an inspection of the clinical site is requested by a regulatory authority, investigators must inform Gilead immediately about this request. It is important that investigators and their relevant personnel are available during the monitoring visits and possible audits or inspections and that sufficient time is devoted to the process. Investigators and institutions will allow the appropriate regulatory authorities direct access to source documents to perform this verification.

9.10. Limitations of the Research Methods

This study has the characteristic disadvantages of retrospective studies, namely, selection bias, information bias, and other confounding variables.

In order to reduce selection bias, subject's eligibility criteria have been well defined, however this is not a type of bias easy to prevent and measure.

Additionally, a propensity score approach (matching or regression) will be considered to balance the covariates in the four cohorts and therefore to reduce the impact of treatment selection bias.

Due to lack of matching procedure, the sub study is subject to selection bias. Information bias can be prevented by using standard measurement instruments, like eCRF. However this study will have a source of information biases related to the possible lack of registry of some data that is impossible to be prevented or reduced.

9.11. Other Aspects

9.11.1. Joint Investigator/Sponsor Responsibilities

9.11.1.1. Access to Information for Monitoring

The study monitor is responsible for review of a sample of the eCRFs at set intervals throughout the study to verify adherence to the protocol and the completeness of the data being entered on the forms. The investigator will provide the study monitor with access to any subject records needed to verify the entries on the eCRFs. The investigator agrees to cooperate with the study monitor to ensure that any problems detected in the course of these monitoring visits are resolved.

9.11.1.2. Study Discontinuation

Both the sponsor and the investigator reserve the right to terminate the study at any time. Should this be necessary, both parties will arrange discontinuation procedures and notify the appropriate regulatory agencies and IECs. In terminating the study, Gilead and the investigator will assure that adequate consideration is given to the protection of the subjects' interests.

10. PROTECTION OF HUMAN SUBJECTS

10.1. Good Pharmacoepidemiology and Pharmacovigilance Practices

The investigator will ensure that this study is conducted in accordance with the principles of the International Conference on Harmonization (ICH) Pharmacovigilance Planning E2E guidelines, and with the laws and regulations of the country in which the research is conducted.

The investigator will conduct this study in accordance with the guidelines of Good Pharmacoepidemiology Practices (GPPs), Heads of Medicines Agencies (HMA) Good Pharmacovigilance Practices (GVP) including archiving of essential documents.

10.2. Independent Ethics Committee (IEC) Review

The sponsor will submit this protocol and any accompanying material to be provided to the subject (such as advertisements, subject information sheets, or descriptions of the study used to obtain informed consent) to an IEC. The investigator will not begin any study subject activities until approval from the IEC has been documented and provided as a letter to the investigator.

Any subsequent modifications made to the protocol or any accompanying material to be provided to the subject after initial IEC approval will also be submitted for IEC approval prior to use.

10.3. Informed Consent

The need for subject's informed consent for retrospective non-experimental studies depends on each country's legislation however, as monitoring of patient records will be performed by Gilead's representative, consent for participation in the study should be obtained.

The investigator is responsible for obtaining written informed consent from each individual participating in this study after adequate explanation of the aims, methods and objectives of the study prior to study participation and before commencing with any study-related activities. The investigator must utilize the most current IEC approved consent form for documenting written informed consent. Each informed consent (or assent as applicable) will be appropriately signed and dated by the subject or the subject's legally authorized representative and the person conducting the consent discussion, and also by an impartial witness if required by IEC or local requirements.

10.4. Confidentiality

The data collected under this study will be treated in compliance with each country law for personal data protection.

The investigator must assure that subjects' anonymity will be strictly maintained and that their identities are protected from unauthorized parties. Only a unique identifier (as allowed by local law) and a unique study identification code should be recorded on any study-related document.

The investigator agrees that all information received from Gilead, including but not limited to this protocol, eCRFs, and any other study information, remain the sole and exclusive property of Gilead during the conduct of the study and thereafter. This information is not to be disclosed to any third party (except employees or agents directly involved in the conduct of the study or as required by law) without prior written consent from Gilead. The investigator further agrees to take all reasonable precautions to prevent the disclosure by any employee or agent of the study site to any third party or otherwise into the public domain.

